## **8.2 Study Treatment Exposure and Compliance**

Each participant will take daily LDA or placebo from the time of randomization until 36 0/7 weeks GA or delivery. Drug compliance will be routinely monitored throughout this period through pill counts and the completion of a medicine compliance form each time the pill supply is replenished. An interval medical obstetrical history will also be taken during these scheduled visits. Study staff will also provide reminders about proper drug administration and the importance of compliance during bi-weekly visits to monitor side effects.

- As a part of the analyses, characteristics of study drug exposure will be summarized by study arm. Characteristics that will be included in this analysis summary include
  - Gestational age at initiation of first dose treated as a binary measure before and after 10 weeks.
  - Gestational age when last dose was taken
  - Number of individuals with dose withheld under clinical direction
  - Percentage of possible days on which dose was taken:

- As a measure of adherence where the number of planned/possible doses excludes any periods where the participants was asked by a health provider or study staff to stop taking the study medication as a result of a medication side effect or unexpected medical event
- As a measure of exposure where the number of planned/possible doses includes all days between randomization and earliest of end of pregnancy and 36 0/7 weeks GA
- Summarize the percent of doses missed for planned doses prior to 16 weeks GA vs. after 16 weeks GA

### **8.3 Protocol Deviations**

Protocol deviations will be summarized by treatment arm and by site with information such as type of deviation, time of occurrence, and reason. Incidence rate of protocol deviations will also be summarized overall and for each protocol deviation category by treatment arm. Incidence rate of protocol deviations will be calculated as: number of deviations divided by the number of participant weeks at the site. The comments section will be reviewed to examine overarching themes, and these will be included in the final report.

### **8.4 Demographic and Baseline Characteristics**

Demographic and baseline clinical characteristics for the study participants will be summarized by treatment group using the general analysis rules describe above for the mITT, ITT, PP and SAF populations. Variables of interest include maternal age, maternal education, gravidity, maternal weight and BMI, previous pregnancy loss, number of antenatal care visits, delivery attendant, delivery location, and type of delivery.

## **9. EFFICACY ANALYSES**

### **9.1 Overview of Efficacy Analysis Methods**

The primary efficacy analyses will be performed using the mITT population. All other efficacy analyses will be performed either using the mITT, ITT or per-protocol population as detailed below. The data will be summarized by treatment arm, overall and by country. All model-based analyses and test-statistics examining the treatment effect will adjust for GN site as a randomization variable. Additional details are presented in the sections below.

### **9.2 Definition of Analysis Variables**

The following table defines each of the effectiveness and process analysis variables.

Variable	Type	Definition
Primary Outcome		
Preterm birth	Binary	
The unit of analysis is the pregnancy delivery with the outcome classified as “Yes” if the delivery is classified as preterm and “No” if not. Preterm is defined as delivery at or after 20 0/7 weeks and prior to 37 0/7 weeks and includes both live births and stillbirths. This definition is consistent with
 

- WHO definition: babies born before 37 completed weeks of pregnancy.

- ACOG definition: Birth occurs between 20 weeks and 37 weeks of pregnancy

 
Analysis Population: mITT

Secondary Outcomes		

Variable	Type	Definition
Preeclampsia and eclampsia (or more appropriately hypertensive disorders of pregnancy)	Binary	
The unit of analysis is the woman randomized to the trial, but the outcome will be defined by the characterization of evidence of hypertensive disorder, including either preeclampsia or eclampsia occurring during the pregnancy. The algorithm for defining this endpoint is included as an addendum to this SAP in HypertensionAlgorithm_V1.1_10052018 (amendments to this algorithm may occur as part of the endpoint adjudication process and will be documented in new versions of this addendum accordingly).
 
 
• Briefly, any of the following will count as evidence of hypertensive disease: 
 
○ Any reported SAE of preeclampsia or eclampsia.
 
○ M NH registry report of hypertensive disease, preeclampsia or eclampsia.
 
○ Reports of elevated blood pressures that meet criteria based on the ACOG 2013 “Hypertension in Pregnancy” Task Force Report at any point after 20 weeks GA. 
 
▪ The only case that will programmatically qualify for evidence of hypertension is: Any individual with 2 consecutive timepoints with <math>\geq 140</math> mm Hg systolic or <math>\geq 90</math> mm Hg diastolic where those timepoints occur more than a week (7 days) apart. The criteria (e.g. elevated systolic or elevated diastolic) must be consistent for the two consecutive visits.
 
 
 
 
 
• For individuals that do meet the above criteria 
 
○ If they have less no reports of elevated blood pressure or a single report of elevated blood pressure that is followed by a normal value, they will not be considered to have evidence of hypertensive disease.
 
○ If they have any other reports of elevated blood pressure, their outcome classification will be adjudicated in a masked manner by clinical experts.
 
 
 
 
Will exclude any MTP but include withdrawals and terminations as data are available. Analysis Population: mITT
 
.

Variable	Type	Definition
Small for Gestational Age	Binary	
The unit of analysis is the infant delivered from each individual pregnancy. The outcome will be classified as “Yes” if the infant is classified as SGA, defined as a newborn with weight below the 10th percentile for gestational age” and “No” otherwise. Note that growth curves appropriate for each GN site based on Intergrowth standards will be used to define the expected gestational age distribution.
 
For any outcomes involving birth weight, the reported weight will only be used to calculate that outcome if collected within 4 days of birth. Any weight captured after 4 days will be excluded.
 
Analysis Population: mITT

Perinatal Mortality	Binary	
The unit of analysis is the infant delivered from each individual pregnancy. The outcome will be classified as “Yes” if the infant is a fresh or macerated stillbirth or a death in the first week of life; the perinatal period commences at 20 completed weeks (154 days) of gestation and ends seven completed days after birth. Pregnancies terminated prior to 20 completed weeks of gestation will be treated as missing for this outcome.
 
Analysis Population: mITT

Variable	Type	Definition
Other Outcomes of Interest—Maternal Outcomes		
Preterm, preeclampsia	Binary	
The unit of analysis is the woman randomized to the trial who delivers after 20 weeks gestational age. The outcome will be defined as delivered at less than 34 weeks GA AND also meeting the criteria for the endpoint “Preeclampsia and eclampsia (or more appropriately hypertensive disorders of pregnancy).”
 
Analysis population: mITT

Vaginal Bleeding	Binary	
The unit of analysis will be individual woman. Per the protocol, Vaginal Bleeding is defined as: “Bleeding during pregnancy (i.e., WHO generally defines as ‘light’ or ‘heavy’ bleeding based on clinical symptoms).” This outcome will be defined based on Question 2e of Form ASP06 and will be classified as “Yes” if the response to this question is Yes at any bi-weekly visit, and No if all completed biweekly visits have either a No or a DK response. Any woman with at least one biweekly visit form will be included in the denominator; the outcome will be classified as missing if a subject has no biweekly visit forms.
 
Analysis population: ITT

Antepartum Hemorrhage	Binary	
The unit of analysis will be individual woman with a delivery after 22 weeks. Per the protocol, antepartum hemorrhage is defined as: “Bleeding from the genital tract at any time after the 22nd week of pregnancy and before the birth of the baby. There are two main causes of antepartum hemorrhage, placenta previa and abruptio placentae.” This outcome will be defined based on Question A8b from Form MN02 from the MNH Registry. The event is defined as follows in the MNH Registry Manual of Operations: “Defined as blood loss of > 1000 cc of blood prior to delivery.”
 
Analysis population: mITT

Variable	Type	Definition
Postpartum Hemorrhage	Binary	
The unit of analysis will be individual woman. Per the protocol, postpartum hemorrhage is defined as: "Blood loss of 1000 ml or more from the genital tract after delivery and up to six weeks post-delivery. Common causes include atony (poor muscle tone) of the uterus or trauma to the genital tract, e.g. tears of the vagina, cervix, or lower segment of the uterus." This outcome will be defined based on Question A8c from Form MN02 or Question B7 from Form MN03 from the MNH Registry. The event is defined as follows in the MNH Registry Manual of Operations: Defined as blood loss of > 1000 cc of blood after delivery prior to six-week visit.
 
Analysis population: Safety

Maternal mortality through 42 days	Binary	
The unit of analysis will be women randomized. Per the protocol, maternal mortality is defined as: "the death of a woman during pregnancy (i.e. conception to delivery) and the puerperium (i.e. up to 42 days after delivery)." The event will be defined as "Yes" if the woman dies prior to 42 days after delivery and "No" otherwise. This outcome measure will be obtained from forms MN02 and MN03 in the MNH Registry. If the 42-day outcome is missing and the woman was alive at the last known follow-up, this outcome will be treated as missing.
 
Analysis population: ITT

Late Abortion	Binary	
The unit of analysis will be individual woman. Per the protocol, late abortion is defined as: "Spontaneous fetal loss <math>\geq</math> 16 weeks." This outcome will be defined based on a response of 4 for Question A7 from Form MN02 from the MNH registry and will be classified as "Yes" if that response is listed as the Mode of Delivery and the pregnancy has a GA of 16 weeks or greater and "No" otherwise. Per the MNH Registry Manual of Operations, that mode of delivery should be used if "A delivery prior to 20 weeks gestation (or <500 g). Miscarriage is also known as spontaneous abortion." If the delivery is after 20 weeks and is classified as a miscarriage on the form, the outcome will be reclassified as a stillbirth. Individuals with loss prior to 16 weeks will be excluded from the analyses.
 
Analysis population: ITT

Variable	Type	Definition
Other Outcomes of Interest—Fetal Outcomes		
Preterm birth <34 0/7 weeks of pregnancy	Binary	
The unit of analysis will be the individual delivered fetus or infant (either live birth or stillbirth); note that per the protocol, the event is defined as: “live birth before 34 0/7 weeks of pregnancy are completed,” so this definition represents a departure from the protocol. This will be defined as a secondary variable in the analysis data set based on gestational age as determined from ASP forms and neonatal outcome as determined from Form MN02 from the MNH Registry.
 
Analysis population: mITT

Birth weight < 2500g	Binary	
The unit of analysis will be the individual infant and per the protocol, the event is defined as: “Birth weight is defined as the first weight of the fetus or newborn obtained after birth. For live births, birth weight should preferably be measured within the first hour of life before significant postnatal weight loss has occurred, recorded to the degree of accuracy to which it is measured (WHO). Birth weight <2500 g is defined as low birth weight” This outcome measure will be a derived measure obtained using the birth weight information provided on Questions C3-C5 from Form MN02 from the MNH Registry. If the actual measure is obtained, the binary variable will be generated from Question C3; otherwise it will be based on the response to Question C5.
 
For any outcomes involving birth weight, the reported weight will only be used to calculate that outcome if collected within 4 days of birth. Any weight captured after 4 days will be excluded.
 
Analysis population: mITT

Variable	Type	Definition
Birth weight < 1500g	Binary	
The unit of analysis will be the individual infant and per the protocol, the event is defined as: "Birth weight is defined as the first weight of the fetus or newborn obtained after birth. For live births, birth weight should preferably be measured within the first hour of life before significant postnatal weight loss has occurred, recorded to the degree of accuracy to which it is measured (WHO). Birth weight <1500 g is defined as very low birth weight." This outcome measure will be a derived measure obtained using the birth weight information provided on Questions C3-C5 from Form MN02 from the MNH Registry. If the actual measure is obtained, the binary variable will be generated from Question C3; otherwise it will be based on the response to Question C5.
 
For any outcomes involving birth weight, the reported weight will only be used to calculate that outcome if collected within 4 days of birth. Any weight captured after 4 days will be excluded.
 
Analysis population: mITT

Fetal Loss	Binary	
The unit of analysis will be the individual delivered fetus or infant and per the protocol, the event of fetal loss is defined as: "Spontaneous loss <math>\geq</math> 16 weeks GA plus perinatal mortality." This binary outcome measure will be defined in the analysis data set based on gestational age as measured via the ASP forms and mortality outcomes as determined from Forms MN02 and MN03 from the MNH Registry. Any death of an infant greater than 16 weeks GA and prior to 7 days post-delivery will be classified as "Yes" and live births classified as alive at 7 days will be classified as "No." Any fetal loss (including MTP or miscarriage) that occurs prior to 16 weeks will be treated as a missing value.
 
Analysis population: ITT

Variable	Type	Definition
Spontaneous abortion	Binary	
The unit of analysis is the individual pregnancy. Per the protocol, the binary outcome of spontaneous abortion is defined as: "Premature expulsion of a non-viable fetus from the uterus at < 20 weeks gestation." This outcome will be defined based on Questions A7-4 or C1 from Form MN02 from the MNH registry and will be classified as "Yes" if the response to A7-4 is listed as the Mode of Delivery or the response to C1. Fetal/Neonatal outcome is answered 1. Miscarriage and "No" otherwise. Per the MNH Registry Manual of Operations, that mode of delivery should be used if "A delivery prior to 20 weeks gestation (or <500 g). Miscarriage is also known as spontaneous abortion."
 
Analysis population: ITT

Stillbirth	Binary	
The unit of analysis will be the individual infant that delivers at 20 weeks gestational age or greater during the specified analysis period. The event will be classified as "Yes" if the infant is classified as a non-macerated still birth or with maceration status unknown via Forms MN02 and MN05 in the MNH Registry and "No" if the baby is born alive as specified via Form MN02 in the MNH Registry. Note that infants classified as Macerated still births are not included in this population. Also note that deliveries classified as miscarriages but that have GA of 20 weeks or greater will be reclassified as stillbirths.
 
Analysis population: mITT

Medical Termination of Pregnancy (MTP)	Binary	
The unit of analysis is the individual pregnancy. Per the protocol, the binary outcome of MTP is defined as: "an operation or other procedure to terminate pregnancy before the fetus is viable." This outcome will be defined based on Question A7-5 or Question from Form MN02 from the MNH registry and will be classified as "Yes" if the response 5 is listed as the Mode of Delivery on Question A7 or if Question C1. Fetal/neonatal outcome is answered 2. MTP and "No" otherwise. Per the MNH Registry Manual of Operations, that mode of delivery should be used if "This response includes any medical termination of pregnancy, including abortion (therapeutic abortion, medical abortion, etc.)."
 
Analysis population: ITT

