### **FETAL OUTCOMES OF INTEREST**

- ***Preterm birth <34 0/7 weeks of pregnancy:*** live birth before 34 0/7 weeks of pregnancy are completed.

- **Birth weight <2500g and Birth weight <1500g:** Birth weight is defined as the first weight of the fetus or newborn obtained after birth. For live births, birth weight should preferably be measured within the first hour of life before significant postnatal weight loss has occurred, recorded to the degree of accuracy to which it is measured (WHO). Birth weight <2500 g is defined as low birth weight, whereas birth weight <1500 g is defined as very low birth weight.
- **Fetal Loss:** Spontaneous loss  $\geq$  16 weeks GA plus perinatal mortality.
- **Late abortion:** Spontaneous fetal loss  $\geq$  16 weeks.
- **Spontaneous abortion:** Premature expulsion of a non-viable fetus from the uterus at  $<$  20 weeks gestation.
- **Stillbirth:** Birth of a baby that shows no signs of life at birth (no gasping, breathing, heart beat or movement). (WHO). It may be a macerated or fresh stillbirth. The signs of maceration are discoloration and peeling of the skin leaving areas of raw tissue. The skull is usually soft, as the brain has become soft. The umbilical cord is usually stained a dark red or black. The amniotic fluid is usually darkly stained. Maceration is the result of the infant being dead for at least 12 hours. Macerated stillborn infants are assumed to have died before the onset of labor. Fresh stillbirths show no sign of maceration and have usually died during labor or shortly before the onset of labor.
- **Medical termination of pregnancy:** an operation or other procedure to terminate pregnancy before the fetus is viable.

**NOTE:** (WHO) at the end of the definition means the definition is from the 2006 WHO guide titled: *Integrated Management of Pregnancy and Childbirth Pregnancy, Childbirth, Postpartum and Newborn Care: A guide for essential practice.*

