### Modified Intention to Treat (mITT) Population

**The primary analysis population will be the modified intention to treat population**, which includes all eligible, randomized participants who provide any post-baseline outcome data and who deliver at 20 weeks gestational age or greater. All participants will be assigned to the arm to which they were randomized irrespective of treatment received. Unless specified otherwise, data for this population will be analyzed as available (i.e. irrespective of protocol deviation occurrence, subsequent study participation termination, or study drug withdrawal). This population will also be used for many of the secondary analyses. Note that this population represents a change from the protocol, which indicates that the ITT population will be used for the primary analyses. This change was made prior to any unmasking.

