## **7.3 Missing Data Approaches:**

The study is likely to have two primary sources of missing data. Since the primary interest is in delivery outcomes for women who deliver after 20 weeks, the first primary source for missing data is early pregnancy losses due to miscarriage or medical termination of pregnancy (MTP) prior to 20 weeks gestational age. The second primary reason for missing data will be participant loss to follow-up. Each of these scenarios is treated separately below.

Women are being enrolled in the ASPIRIN trial when they are between 6 0/7 weeks and 13 6/7 weeks gestational age. Depending on the distribution of study participants over this gestational age range we anticipate that between 2% and 8% of the women in the study will have a pregnancy loss prior to 20 weeks. For the primary outcome of preterm birth, these women will be excluded from the analyses and hence be considered missing at random. However, because we recognize that these women may not have the same risk of preterm delivery as those followed past 20 weeks, we will generate two additional sensitivity analyses to assess whether inference is robust to this assumption. For the first analyses, these early terminations will be treated as preterm deliveries in a full ITT analysis. For the second approach, the MITT population will be used with inverse probability weighting used to account for the individuals lost prior to 20 weeks.

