## 9.5 Secondary Outcome Analyses

This study has been designed to evaluate the differences between the two treatment arms for three secondary outcomes: the risk of perinatal mortality; the risk of eclampsia/preeclampsia, and the risk of a SGA delivery. As with the primary analyses, each of these outcomes will be examined individually using descriptive tests of hypotheses that the risk differs between the two arms based on Cochran-Mantel-Haenszel tests stratified by Global Network sites. The analyses for each of these 3 secondary outcomes will utilize the same modified intention-to-treat population used for the primary outcome. Each of these hypothesis tests will be conducted at the 0.05 level of significance with no adjustment for multiple comparisons. In addition to this set of hypothesis tests, model-based analyses comparable to those conducted for the primary analyses will be used to evaluate potential heterogeneity of treatment effect across sites and evaluate potential confounding. For each of the 3 outcomes, an initial model will include terms for treatment, site, and a treatment by site interaction. If the treatment by site interaction term is found to be significant ( $p<0.05$ ), then all subsequent models will include the interaction term and all effects will be reported by site; because the study will lack power to detect site-specific effects, all p-values will be reported for the average effect and site effects will include point and interval estimates. If the interaction term is not significant, it will be removed from the model and this initial model be used to estimate an unadjusted treatment effect controlling for site. The second series of models will include any demographic or clinical variable found to differ significantly between the treatment arms in the preliminary analyses described above. These models

will be used to generate adjusted estimates of the treatment effect controlling for potential confounders.

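### The hypertensive-disorder outcome excludes medical terminations with no gestational-age limit, so within the mITT set it drops women terminated at 20 weeks or later, when the outcome can first arise

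*Combined protocol and SAP*

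**What the plan says.** The hypertensive-disorder row of the table in SAP 9.2 takes the randomised woman as its unit and mITT as its population. After the case criteria it adds: "Will exclude any MTP but include withdrawals and terminations as data are available". No gestational age is attached to the MTP part.

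Five other places bear on this:

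- SAP 5 limits mITT to eligible, randomised participants "who provide any post-baseline outcome data and who deliver at 20 weeks gestational age or greater".
- SAP 7.3 names as its first source of missing data "early pregnancy losses due to miscarriage or medical termination of pregnancy (MTP) prior to 20 weeks gestational age", and excludes these women from the primary analysis.
- SAP 9.5 says of perinatal mortality, preeclampsia/eclampsia and SGA: "The analyses for each of these 3 secondary outcomes will utilize the same modified intention-to-treat population used for the primary outcome". Protocol 3.1.2 says the same.
- Protocol Appendix 3 defines MTP as "an operation or other procedure to terminate pregnancy before the fetus is viable". It sets the limit by viability and gives no week.
- The preterm-preeclampsia row of SAP 9.2 counts a woman who "delivered at less than 34 weeks GA AND also meeting the criteria for the endpoint" of hypertensive disorder.

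**The concern.** Within a population that already excludes pregnancies ending before 20 weeks, an exclusion of any MTP has only later MTPs left to act on. SAP 3.2 counts new-onset hypertension beyond 20 weeks and preeclampsia after the 20th week, so these women are removed in the period when the outcome can first occur. Termination happens after randomisation, and severe hypertensive disease is one possible reason for it. A woman with a reported preeclampsia SAE already meets the case definition, yet she leaves both numerator and denominator if her pregnancy is then recorded as an MTP.

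The comparison of arms on this outcome is at stake. If the share of cases lost differs between arms, the relative risk is biased. Preterm preeclampsia refers to the same endpoint and, being a subset of it, has fewer events, so any loss there would weigh more.

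**Working it through.** **What the clause can remove**

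1. mITT (SAP 5) requires delivery at 20 weeks or later, and SAP 7.3 has already set aside MTPs before 20 weeks. For those earlier MTPs the clause adds nothing.
2. MTPs at 20 weeks or later can be in the data. Appendix 3 stops at viability, not at 20 weeks. The MTP row of SAP 9.2 uses the registry's mode-of-delivery code, whose quoted definition has no gestational-age limit.
3. Miscarriages recorded at 20 weeks or later are reclassified as stillbirths (late-abortion and stillbirth rows). There is no matching rule for MTP, so an MTP label at that age stands.
4. The perinatal-mortality row treats as missing only pregnancies terminated before 20 completed weeks. The hypertensive-disorder row has no such limit.
5. The same sentence keeps withdrawals and terminations as far as data exist, so incomplete follow-up does not explain the MTP exclusion. SAP 12 does not list it as a change from the protocol, and no rationale or sensitivity analysis for it is given.

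**The plan's own power figures**

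Inputs from SAP 6.2: n = 5,483 per arm, control risk p1 = 5%, alpha 0.05 per comparison. Two-sided testing is assumed; SAP 7.5 states it for the primary test. With p̄ the mean of p1 and p2,

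power = Φ{ [(p1 − p2) − 1.96·√(2p̄(1 − p̄)/n)] / √([p1(1 − p1) + p2(1 − p2)]/n) }.

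For a 20% reduction, p2 = 0.04 and p̄ = 0.045. The numerator is 0.0100 − 1.96 × 0.00396 = 0.00224 and the denominator is 0.00396, so power = Φ(0.566) = 71.4%. Reductions of 24% and 26% give 86.5% and 91.6%. The SAP states 70%, 85% and 90%; with a continuity correction the results are 69.8%, 85.5% and 90.8%. The planning figures reproduce.

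**Illustration of the exclusion**

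Expected cases are 0.05 × 5,483 = 274 on placebo and 0.04 × 5,483 = 219 on aspirin, a relative risk of 0.80. Let f1 and f2 be the shares of cases ending in an MTP at 20 weeks or later. **These shares are assumptions; the documents give none.** Removed women leave numerator and denominator, so the risk in an arm with e cases becomes (e − f·e)/(n − f·e). Power uses the same formula, with the remaining n in each arm.

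| f1 placebo / f2 aspirin | Women removed | RR | Power |
|---|---|---|---|
| 0 / 0 | 0 / 0 | 0.800 | 71.4% |
| 2% / 2% | 5.5 / 4.4 | 0.800 | 70.6% |
| 5% / 5% | 13.7 / 11.0 | 0.800 | 69.3% |
| 10% / 10% | 27.4 / 21.9 | 0.799 | 67.1% |
| 2% / 0 | 5.5 / 0 | 0.816 | 63.2% |
| 5% / 2% | 13.7 / 4.4 | 0.824 | 57.7% |
| 5% / 0 | 13.7 / 0 | 0.840 | 49.5% |
| 0 / 5% | 0 / 11.0 | 0.762 | 86.0% |

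Worked row, 5% / 0: (274.15 − 13.71)/(5,483 − 13.71) = 0.0476, and 0.0400/0.0476 = 0.840.

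Equal shares leave the relative risk unchanged even though more placebo women are removed (13.7 against 11.0 at 5%). Bias needs unequal shares, not just unequal counts.

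**The case against.** The clause may be redundant. The row's unit is the randomised woman, so the sentence could simply restate that early terminations drop out. If an MTP is not a delivery for mITT, nobody further is removed. The coding of MTP as a mode of delivery speaks against this reading. So, more weakly, does the MTP line under delivery mode in the SAP's baseline table: that shell serves ITT and mITT together and also lists miscarriage. Even if the reading were right, women with an MTP at 20 weeks or later would still be missing from this outcome.

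The conflict with SAP 9.5 is soft, and that part of the objection stands. Other mITT outcomes carry their own evaluability rules: SGA drops weights taken after 4 days, and antepartum haemorrhage is limited to deliveries after 22 weeks. A reader might infer a flat contradiction, but SAP 9.5 does not promise identical denominators. The clause merely sits poorly with it.

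A reader might also infer that the earliest and most severe cases are being deleted and that the effect is therefore pulled toward no difference. The documents do not show this. They give no count of MTPs at 20 weeks or later and no reason for any. Appendix 3 confines MTP to the period before viability, so an indicated delivery after viability is not an MTP by that definition and stays in. The direction of any bias is open.

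Nor do the documents say that preterm preeclampsia loses the same women. Its row imports the endpoint's criteria and states its own unit and population; whether the exclusion comes with them is unclear.

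Finally, MTP is reported by arm in the ITT population, preeclampsia/eclampsia SAEs are tabulated in the safety population, and selected secondary outcomes go through masked review. These make the problem more visible but do not return the women to the test or the relative risk. The full hypertension algorithm is in an addendum not included in these documents and may qualify the rule.

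**Conclusion.** The point holds as a defect in the outcome definition. As written, the clause in practice excludes women from the hypertensive-disorder analysis because of an MTP between 20 weeks and viability, a post-randomisation event that the outcome may cause. It is inconsistent with the perinatal-mortality row and is unexplained.

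Its size cannot be established from the documents and is probably small. Equal loss across arms costs about 2 points of power at an assumed 5% of cases and leaves the relative risk at 0.80. Unequal loss could bias the estimate either way: 0.84 or 0.76 when 5% of cases are lost from placebo only or from aspirin only. These figures rest on the SAP's 5% risk and 5,483 per arm, a true 20% reduction, removal of cases only, and assumed shares. SAP 7.5 treats all secondary outcomes as exploratory, so the formal conclusion on preterm birth is not touched. Carry-over to preterm preeclampsia is possible but not stated.

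**What to change.** In the hypertensive-disorder row of SAP 9.2, delete the MTP exclusion or limit it to MTP before 20 0/7 weeks, which mITT already achieves. State that women with an MTP at 20 weeks or later stay in the denominator and are classified by the existing SAE, registry and blood-pressure criteria, using data up to the termination. Say that the same applies to preterm preeclampsia. Check the hypertension-algorithm addendum and make it consistent. Report the number of MTPs at 20 weeks or later by arm, so that a reader can see how much the rule matters.

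The cost is one clause in SAP 9.2, one sentence in the preterm-preeclampsia row, a check of the addendum, and one line in a table. The data are already collected.
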